8.1. General Considerations

Statistical analysis of this study will be the responsibility of Lilly or its designee. All tests of treatment effects will be conducted at a 2-sided alpha level of 0.05, unless otherwise stated, and all confidence intervals (CIs) will be given at a 2-sided 95% level, unless otherwise stated. Endpoints and analyses are defined for the core study period, ie study period with randomized treatment before crossover, unless otherwise specified. Statistical analysis will be performed using SAS software (SAS, version 9.1.2 or higher).

Continuous variables will be summarized using descriptive statistics (ie, number of patients, mean, median, standard deviation, minimum, and maximum). Categorical variables will be summarized by frequency and their corresponding percentage.

Any change to the data analysis methods described in the protocol will require an amendment ONLY if it changes a principal feature of the protocol. Any other change to the data analysis methods described in the protocol, and the justification for making the change, will be described in the clinical study report. Additional exploratory analyses of the data will be conducted as deemed appropriate.

8.1.1. Definitions

Definitions of efficacy, safety, and patient-reported outcome (PRO) analysis variables are listed in respective sections of the SAP. Other variables are listed below alphabetically:

- Age (years): $(\text{informed consent date} - \text{date of birth} + 1)/365.25$; birth month and day are imputed to be 01 July, because only the birth year is collected through electronic case report form (eCRF).
- Baseline Measurement: unless otherwise specified, the last nonmissing measurement prior to the first dose of study drug for safety and tolerability analyses, and the last nonmissing measurement prior to randomization for baseline and efficacy analyses.
- Crossover Baseline Measurement: unless otherwise specified, the last nonmissing measurement prior to the first dose of selpercatinib during crossover period for safety, tolerability, and efficacy analyses.
- Duration: duration is calculated as:
 - Duration (days): $(\text{end date} - \text{start date} + 1)$
 - Duration (weeks): $(\text{end date} - \text{start date} + 1)/7$
 - Duration (months): $(\text{end date} - \text{start date} + 1)/30.4375$
(days in months = $(1/12) * \text{average number of days in a year}$)
 - Duration (years): $(\text{end date} - \text{start date} + 1)/365.25$
- Duration of disease: $(\text{randomization date} - \text{diagnosis of cancer date} + 1)$.
- Study Day (safety and tolerability analyses): study day is calculated as assessment date – first dose date + 1 day if the assessment is done on or after the first dose day. If the assessment is done prior to the first dose day, the study day will be calculated as assessment date – first dose date. Date of first dose is defined as Study Day 1.

- Study Day (baseline and efficacy analyses): study day is calculated as assessment date – randomization date + 1 day if the assessment is done on or after randomization. If the assessment is done prior to randomization, the study day will be calculated as the assessment date – randomization date. Date of randomization is defined as Study Day 1.
- Time-to-Event: the event or censoring time (days) is calculated as the date of event/censoring – randomization date + 1.

8.1.2. Handling of Dropouts or Missing Data

All analyses and descriptive summaries will be based on the observed data. Unless otherwise specified, missing data will not be imputed or “carried forward”. Rules for handling dropouts or missing data are listed by type of analysis alphabetically.

- Adverse event (AE) or concomitant therapy:
 - The missing day of onset of an AE or start date of a concurrent therapy will be set to:
 - first day of the month that the event occurred, if the onset yyyy-mm is after the yyyy-mm of first study treatment;
 - the day of the first study treatment, if the onset yyyy-mm is the same as yyyy-mm of the first study treatment; or
 - the date of informed consent, if the onset yyyy-mm is before the yyyy-mm of the first treatment.
 - The missing day of resolution of an AE or end date of a concurrent therapy will be set to:
 - the last day of the month of the occurrence. If the patient died in the same month, then set the imputed date as the death date.
 - If the onset date of an AE or start date of a concurrent therapy is missing both the day and month, the onset date will be set to:
 - 01 January of the year of onset, if the onset year is after the year of the first study treatment;
 - the date of the first treatment, if the onset year is the same as the year of the first study treatment; or
 - the date of informed consent, if the onset year is before the year of the first treatment.
 - If the resolution date of an AE or end date of a concurrent therapy is missing both the day and month, the date will be set to:
 - 31 December of the year of occurrence. If the patient died in the same year, then set the imputed date as the death date.
 - If the date is completely missing, then no imputation will be done and the event will be considered as treatment-emergent with unknown onset date, unless the end date rules out the possibility.
- Diagnosis date, the following conventions will be used for imputing partial dates:
 - If only the day of the month is missing, the 15th of the month will be used to replace the missing day.

- If both the day and the month are missing, “Jul 1” will be used to replace the missing information.
- General rule for imputing other dates:
 - If only the day is missing, then assign Day 15 of the month, or the date of death if the patient died prior to 15th of the same month to the day.
 - If month is missing, then the date will be set to July first of the year, or the date of death if the patient died prior to July first of the same year.

However, in all cases, after imputation, check if the imputed date is logically consistent with other relevant date variable(s) and make appropriate correction if necessary.

- Relationship: missing classifications concerning relationship will be considered as related to study medication.
- Time-to-event analysis: all censored data will be accounted for using appropriate statistical methods.

8.2. Participant Disposition

A detailed description of participant disposition will be provided according to the Consolidated Standards of Reporting Trials (CONSORT) publishing requirements, including a summary of the number and percentage of patients entered into the study, enrolled in the study, and treated, as well as number and percentage of patients completing the study, or discontinuing (overall and by reason for discontinuation).

8.2.1. Protocol Deviations

Important protocol deviations (IPDs) that could potentially compromise the data integrity and patients’ safety will be summarized for the intention to treat (ITT) population. These deviations will include deviations that can be identified programmatically and those that can only be identified by the clinical research associate during monitoring. Important protocol deviations are described in the Trial Issue Management Plan (TIMP) within the study Trial Master File.

The list of IPDs that could potentially affect the efficacy conclusions of the study will be defined and documented in the TIMP prior to the final database lock in order to identify patients to be excluded from the per-protocol (PP) population.

8.3. Primary Endpoint Analyses

8.3.1. Research Objective and Question

The primary research objective and question is: What is the difference in PFS time between selpercatinib and cabozantinib/vandetanib as the first line therapy in patients with progressive, advanced, kinase inhibitor-naïve, RET-mutant MTC.

8.3.2. Definition of Endpoint

The estimand for the primary objective is described by the following attributes:

- Population: patients with progressive, advanced, kinase inhibitor-naïve, RET-mutant MTC. Further details can be found in Protocol Section 5 Study Population.
- Endpoint: progression-free survival confirmed by BICR, which is defined as the time from randomization until the occurrence of documented disease progression by the BICR, per RECIST 1.1 criteria, or death from any cause in the absence of BICR-documented PD.
- Treatment condition: the randomized study intervention (selpercatinib or cabozantinib/vandetanib) will be administered twice or once a day in continuous 28-day cycles until disease progression, unacceptable toxicity or other protocol-defined reasons for treatment discontinuation. Further details on study interventions including interventions, concomitant therapy and dose modification can be found in Protocol Section 6 Study Intervention.
- Intercurrent-event strategies (IES) for main analytical approach are listed in [Table JZJB.1](#).
- Population-level summary measure: hazard ratio of PFS in selpercatinib versus cabozantinib/vandetanib estimated using a stratified Cox regression model (Cox 1972)

Table JZJB.1. Intercurrent Events of PFS

Intercurrent Event	IES
Study intervention discontinuation prior to PFS event	“Treatment policy” strategy: regardless of whether or not study intervention discontinuation had occurred
Post study intervention discontinuation anticancer therapy prior to PFS event	“While on treatment” strategy: consider the assessment of endpoint up until the time that post study intervention discontinuation anticancer therapy is taken
Extended time without adequate assessment prior to PFS event	“While on treatment” strategy: consider the assessment of endpoint up until the occurrence of extended time without adequate assessment

Abbreviation: IES = intercurrent-event strategies; PFS = progression-free survival.

Rationale for IES: The interest lies in the treatment effect without the confounding effect of other anticancer therapy or extended time without adequate assessment.

- Study intervention discontinuation due to reasons other than PFS event is handled with treatment policy as it reflects clinical practice. Time from randomization until disease progression or death regardless of study intervention discontinuation will be considered in analysis.
- A post study intervention discontinuation anticancer therapy taken prior to PFS event will confound the treatment effect of selpercatinib in terms of PFS. If the anticancer therapy is taken, future disease progression/death status is not needed. The participant will be censored and only the time prior to the post study intervention discontinuation anticancer therapy will be considered in analysis.

- PFS event observed after an extended time without adequate tumor assessment may have occurred much earlier but is not reported because the scheduled assessment was not done. This inadequate observation may introduce bias to PFS estimates. If extended time without adequate assessment occurs, the participant will be censored and only the time up to the last adequate tumor assessment will be considered in analysis.

8.3.3. Main Analytical Approach

PFS by BICR will be compared between treatment arms using the Cui, Hung, and Wang (CHW) testing procedure (Cui et al. 1999) to control the type I error at an overall 1-sided 2.5% significance level:

- At the interim efficacy analysis, the PFS by BICR will be compared using a conventional stratified logrank test, stratified by the 2 randomization strata based on interactive web-response system (IWRS) data: RET mutation (M918T vs. other) and intended control treatment (cabozantinib vs. vandetanib).
- At the final analysis, the PFS by BICR will be compared using a CHW test as described below. If the re-estimated total number of events is equal to the initial planned total number of events, the CHW test will be reduced to the conventional stratified logrank test.

Table JZJB.2. Defining the Values for Computing the CHW Test Statistic of PFS

Quantity	Input Value or Derivation / Calculation
$Z_{PFS,1}$	This is the stratified logrank test statistic comparing PFS between treatment arms at the interim analysis. The interim analysis is triggered after approximately 56 PFS events have occurred (at 75% information fraction).
$Z_{PFS,2}$	This is the stratified logrank test statistic comparing PFS between treatment arms at the final analysis.
$e_{PFS,1}$	This is the observed number of PFS events across both treatment arms at the interim analysis. The interim analysis is triggered after approximately 56 PFS events have occurred (at 75% information fraction). Due to the uncertainty in operation, the exact timing of the interim may occur at a number of events slightly smaller or larger than the planned 56 number of PFS events.
$e_{PFS,2}$	This is the number of PFS events across both treatment arms at the final analysis should the study remain at the initial planned total number of events. $e_{PFS,2} = 74$
$e_{PFS,2}^*$	This is the observed number of PFS events across both treatment arms at the final analysis.

Given the quantities defined in Table JZJB.2, the final CHW test statistic for the primary efficacy analysis (at the final analysis after the sample size re-estimation) can be written as a weighted combination of the independent increments comprising the interim stratified logrank test statistic and the post-interim stratified logrank test statistic (Cui et al. 1999):

$$Z_{PFS,CHW} = \sqrt{\frac{e_{PFS,1}}{e_{PFS,2}}} Z_{PFS,1} + \sqrt{\frac{e_{PFS,2} - e_{PFS,1}}{e_{PFS,2}}} \left\{ \frac{\sqrt{e_{PFS,2}^*} Z_{PFS,2} - \sqrt{e_{PFS,1}} Z_{PFS,1}}{\sqrt{e_{PFS,2}^* - e_{PFS,1}}} \right\}$$

As pointed out by Cui, Hung, and Wang (Cui et al. 1999), for group sequential test based on the repeated significance test that can be asymptotically expressed as a Brownian motion process, eg logrank test, with independent increment property, if the conventional logrank statistic is replaced by the CHW statistic while using the original rejection boundary for the conventional logrank statistic, the new CHW test will have the total type I error preserved at the specified level. Therefore, to determine the statistical significance at the final analysis, the $Z_{PFS,CHW}$ will be compared to the Z scale critical boundary -1.960 given in Section 8.8 Interim Analysis.

In addition, unadjusted HR between treatment arms will be estimated using a stratified Cox regression model (Cox 1972), stratified by randomization strata. Progression free survival curves, medians, and PFS rates at various time points with 95% CI for each treatment arm will be estimated using the Kaplan-Meier method (Kaplan and Meier 1958).

Table JZJB.3 defines censoring rules to be applied to the BICR PFS main analysis.

Table JZJB.3. PFS Censoring Scheme

Situation	Event/Censor	Date of Event or Censor
Tumor progression ^a by BICR or death	Event	Earliest date of PD by BICR or death
No tumor progression by BICR and no death	Censored	Date of last adequate tumor assessment ^b , per RECIST 1.1 criteria, or date of randomization (whichever is later)
No baseline radiologic tumor assessment available	Unless	
No adequate postbaseline tumor assessment available	Censored	Date of randomization
and death reported after 2 scan intervals ^c following randomization	Censored	Date of randomization
New systemic anticancer therapy	Censored	Date of adequate tumor assessment, per RECIST 1.1 criteria, prior to start of new therapy or date of randomization (whichever is later)
Tumor progression by BICR or death documented immediately after 2 or more missing scan intervals following last adequate tumor assessment or randomization (whichever is later)	Censored	Date of last adequate tumor assessment, per RECIST 1.1 criteria, or date of randomization (whichever is later)

Abbreviations: BICR = blinded independent central review; CR = complete response; PD = progressive disease; PFS = progression-free survival; PR = partial response; RECIST 1.1 = Response Evaluation Criteria in Solid Tumors, version 1.1, SD = stable disease.

^a Symptomatic deterioration (that is, symptomatic progression that is not radiologically confirmed per RECIST 1.1 criteria) will not be considered as tumor progression.

^b Adequate tumor assessment per RECIST 1.1 criteria refers to an assessment with 1 of the following responses: CR, PR, SD, or PD.

^c The 2-scan interval is counted from the date of last adequate tumor assessment to the date of next 2 scheduled tumor assessments plus 14 days (adjusted by tumor assessment window).

- If there are multiple dates associated with 1 assessment, the assessment date will be set to the first date when the overall response is PD and the last date otherwise.

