5.1. Inclusion Criteria

Participants are eligible to be included in the study only if all of the following criteria apply:

Age

1. Are of an acceptable age to provide informed consent according to local regulations and are at least 18 years of age (patients as young as 12 years of age will be allowed if permitted by local regulatory authorities and institutional review boards).
 - a. All patients of 12 years of age and older, after giving assent / legally designated representative/ participant written consent.

Type of Participant and Disease Characteristics

2. Histologically or cytologically confirmed, unresectable, locally advanced and/or metastatic MTC and no prior history of treatment with kinase inhibitors for advanced/metastatic disease.
 - a. Prior systemic (agents other than kinase inhibitors) or radiation therapy occurring >14 months before enrollment is allowed. Prior systemic therapy or radiation therapy within the 14 months before enrollment may be allowed with discussion and approval by the Lilly medical team.
 - b. Patients with prior kinase inhibitor therapy of less than 7 days and discontinued for reasons other than intolerance or progression may be allowed with approval by the Lilly medical team.
 - c. Patients with mixed histology (e.g., incidental papillary thyroid cancer identified at the time of resection) are eligible if MTC is the dominant histology.
3. Radiographic progressive disease per RECIST 1.1 (Eisenhauer et al. 2009) at screening compared with a previous image taken within the prior 14 months as assessed by the BICR. Patients with measurable or non-measurable but evaluable disease are eligible; however, patients with non-measurable disease may not have disease limited to bone sites only.

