8.3.4. Sensitivity Analyses

Multiple sensitivity analyses for the PFS by BICR will be conducted as defined below:

- discounting the event of PD if pleural effusion is the only reason of PD per BICR and the patient is experiencing chylous effusion at the time of PD (see Sensitivity Analysis [SA] 6 [Table JZJB.4](#));
- ignoring new systemic anticancer therapy (see SA2 [Table JZJB.4](#)) according to the EMA guidelines of censoring scheme (EMA 2012);
- using other rules for censoring (as defined by [Table JZJB.4](#));
- using an unstratified logrank test and an unstratified Cox regression model;
- using stratification factors based on the eCRF data;
- repeating the main PFS by BICR analysis for the PP population.

Table JZJB.4. PFS Censoring Scheme - Sensitivity Analyses

Definition	Situation	Event/ Censor	Date of Event or Censor
SA1: Ignoring absence of adequate postbaseline tumor assessment	No adequate postbaseline tumor assessment available and death reported after 2 scan intervals following randomization	Event	Death
SA2: Ignoring new systemic anticancer therapy	New systemic anticancer therapy and: 1. No tumor progression by BICR and no death 2. Tumor progression by BICR or death after start of new therapy	1. Censored 2. Event	1. Date of last adequate tumor assessment, per RECIST 1.1 criteria, or date of randomization (whichever is later) 2. Earliest date of PD or death
SA3: Considering events right after the new systemic anticancer therapy starts	Tumor progression by BICR or death within next 14 days from the start of new systemic anticancer therapy	Event	Earliest date of PD by BICR or death
SA4: Ignoring missing tumor assessments	Tumor progression by BICR or death documented after 2 or more missing scan intervals following last adequate tumor assessment or randomization (whichever is later)	Event	Earliest date of PD by BICR or death
SA5: Considering lost to follow up as tumor progression	Patient lost to follow up and no tumor progression by BICR and no death	Event	Date of next scheduled tumor assessment at or after patient was lost to follow up
SA6: Discounting PD confounded by chylous effusion	Pleural effusion is the only reason of PD per BICR and the patient is experiencing chylous effusion at the time of PD	Censor	Date of last adequate tumor assessment, per RECIST 1.1 criteria

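### Does the closed list of adequate tumor responses throw away follow-up for patients with non-measurable disease in the primary PFS analysis?

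*SAP*

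**What the plan says.** SAP Table JZJB.3 censors a patient with "No tumor progression by BICR and no death" at the last adequate tumor assessment or at randomization, whichever is later. Footnote b defines the key term: "Adequate tumor assessment per RECIST 1.1 criteria refers to an assessment with 1 of the following responses: CR, PR, SD, or PD". Table JZJB.7 repeats this for TFFS, and SAP 8.4.2 carries the same methods to the investigator-assessed versions. Protocol 9.4.3.1 uses the term without defining it.

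Protocol 5.1, criterion 3, states: "Patients with measurable or non-measurable but evaluable disease are eligible". Non-measurable disease confined to bone is excluded.

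Two other rules in Table JZJB.3 rest on the same term. A patient with "No adequate postbaseline tumor assessment available" whose death is reported more than two scan intervals after randomization is censored at randomization. Progression or death straight after two or more missing scan intervals is censored at the last adequate assessment, and under footnote c "The 2-scan interval is counted from the date of last adequate tumor assessment". SAP 8.3.2 explains this second rule: the event may have happened earlier but "is not reported because the scheduled assessment was not done".

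Table JZJB.4 includes "SA1: Ignoring absence of adequate postbaseline tumor assessment" and "SA4: Ignoring missing tumor assessments". Protocol 6.3 leaves BICR details to a separate charter, which is not among the documents.

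**The concern.** Footnote b defines adequacy by response label, not by whether the scan was done and could be read. The list is closed, and the trial enrols patients who may have no target lesions. Suppose the central reader or the site records a stable scan in such a patient under a label other than SD, for example non-CR/non-PD (a term that neither document uses). On a literal reading, an event-free patient with every scan done contributes no follow-up, and a late death without progression is censored on day 1. Early events still count, so whether a patient's time is used would depend on the outcome. SA1 and SA4 bring back late deaths and late progressions, but no planned analysis brings back the event-free follow-up. The primary endpoint and a key secondary endpoint share the rule.

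**Working it through.** **1. What the text supports.** The harm needs two conditions: a label other than SD for stable disease without target lesions, and literal use of footnote b on it.

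- Neither document contains such a label. SAP 8.4.2 defines disease control as CR, PR or SD lasting at least 16 weeks, over all randomized patients, with no separate stable category for patients without target lesions.
- Below Table JZJB.3, assessment dates are split into PD and everything else. Protocol 8.1.2 sorts investigator readings into progression and non-progression.
- SAP 8.3.2 aims the missing-assessment rule at scans that were not done. A scan that was performed and read is not missing.
- The row on absent postbaseline assessments is not a free-standing rule. It is joined to a late death, as SA1 and the matching row of Table JZJB.7 confirm. Day-1 censoring of event-free patients would therefore come only from the whichever-is-later clause.

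**2. The plan's own figure.** Inputs from SAP 4.2 and 6: HR 0.5, 1-sided 2.5%, 80% power, 2:1 allocation. Events = (1.960 + 0.842)² / [(2/3)(1/3)(ln 0.5)²] = 7.85 / (0.2222 × 0.4805) = 73.5, so 74. Power at 74 events = Φ(√(74 × 2/9) × 0.693 − 1.960) = Φ(0.851) = 80.3%. The plan's figure reproduces.

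**3. Patients affected if both conditions held.** The share of such patients is not given; 5%, 10% and 20% are assumed. Event-free at the 74-event cutoff: 250 − 74 = 176. Moved to day 1: 176 × 0.05 = 8.8; × 0.10 = 17.6; × 0.20 = 35.2.

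**4. Effect on the analysis.** Simulation of 4,000 trials per share: 250 patients, 2:1, exponential PFS with medians of 50 and 25 months, scans every 8 weeks to week 24 and then every 12 weeks, cutoff at the 74th true event. Assumed, not in the documents: 24-month accrual, and 10% of events being deaths. Two scan intervals from randomization are 16 weeks plus 14 days.

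*Late progression counted:*

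| Share | Events kept | HR, all scans adequate | HR, literal reading | Shift | 24-month PFS, Arm A | 24-month PFS, Arm B |
|---|---|---|---|---|---|---|
| 5% | 73.5 | 0.505 | 0.508 | 0.003 | 0.731 → 0.722 | 0.534 → 0.522 |
| 10% | 73.2 | 0.505 | 0.511 | 0.006 | 0.731 → 0.712 | 0.532 → 0.509 |
| 20% | 72.6 | 0.508 | 0.522 | 0.014 | 0.731 → 0.689 | 0.534 → 0.483 |

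*Late progression also censored (power by the formula in step 2):*

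| Share | Events kept | Power | HR | Delay to 74 events |
|---|---|---|---|---|
| 5% | 70.9 | 78.6% | 0.505 | 0.98 months |
| 10% | 68.0 | 76.9% | 0.505 | 2.12 months |
| 20% | 62.3 | 73.2% | 0.509 | 4.86 months |

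With 12- or 36-month accrual, or 30% of events being deaths, the events kept in the second table stay within 70.8–71.1, 67.9–68.2 and 62.3–62.4.

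**5. Direction.** A second simulation (1,500 trials per setting, 30-month accrual, 167 and 83 patients) moved 25.7 patients in Arm A and 9.8 in Arm B to day 1 at the 20% share: 25.7/167 = 15.4% against 9.8/83 = 11.8%. More event-free time is lost from Arm A, so the HR moves toward 1. With late progression counted, that simulation's HR went from 0.510 to 0.518, 0.518 and 0.531, and its power from 0.851 to 0.835, 0.831 and 0.813. Its starting power is above the formula's 80.3%, so these figures should be compared only with each other.

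**The case for a change.** The best case for acting is that an SAP should be executable as written. The footnote governs the primary endpoint, the list is closed, the trial expressly admits these patients, and no sensitivity analysis restores the event-free time. In an open-label trial, leaving the mapping to whoever builds the dataset is untidy, and one phrase would settle it at no cost.

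Part of this stands. Neither document states the label, and SA1 and SA4 do not reach event-free patients. But the argument shows only that a detail is unwritten in these two documents. It does not show that any scan would be labelled outside the four categories, and the charter that sets response coding cannot be seen here. The literal outcome also needs an analyst to treat a performed, readable, progression-free scan as no assessment, against the rationale in SAP 8.3.2. The mapping concerns BICR readings, which are blinded, and the resulting shift is toward no effect, so no route to a false positive is shown.

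**Conclusion.** No change to the plan. This is a gap that analysts would fill sensibly: a readable scan without progression in a patient who has no target lesions counts as SD, the only stable category the SAP uses. Coded that way, nothing is lost. Under the literal reading with late progression counted, the HR would move by about 0.003, 0.006 or 0.014 toward no effect at shares of 5%, 10% or 20%. The heavier case, about 62 events and 73% power at an unchanged cutoff, needs the 20% share and the disfavored reading of the missing-scan rule. These sizes rest on the assumed shares, accrual and death fraction, and on exponential PFS at the planned medians. The conclusion would change only if the BICR Charter or the investigator form were shown to use another label with no mapping to SD.
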